### SYMPTOM SURVEY

Think about how your eyes have felt **during a typical day in the last week**. Then, using the scales provided below, please mark a vertical line at the place that best describes your experience with these symptoms during this time period:

#### 1. Watery Eyes

No watering Maximum watering  
0 \_\_\_\_\_ 100

#### 2. Grittiness/Foreign Body Sensation

No grittiness/foreign body sensation Maximum  
0 \_\_\_\_\_ 100

#### 3. Dryness

No dryness Maximum dryness  
0 \_\_\_\_\_ 100

#### 4. Blurry/Fluctuation Vision

No blurry/fluctuating vision Maximum  
0 \_\_\_\_\_ 100

#### 5. Overall Ocular Pain/Discomfort

No ocular pain/discomfort Maximum  
0 \_\_\_\_\_ 100

#### 6. On average, how many times per day did you use eye drops during the past week?

\_\_\_\_\_

### HEALTH AND WELLBEING SURVEY

1. Since your last visit, have you:

- a) Been hospitalized? Yes / No
- b) Used any new medication or changed medication regimens? Yes / No
- c) Experienced any Gastrointestinal irritation e.g. diarrhea, heartburn, bloating or nausea? Yes / No
- d) Experienced unusual bleeding? Yes / No
- e) If you answered yes to any of the above, please explain:

---

---

---

---

2. On average, how many times per day did you ingest the study product during the past week?

---

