# 1. PROTOCOL SYNOPSIS

Table 1

Protocol Title	The effects of dietary supplementation with a combination of flaxseed oil, borage oil and fish oil omega-3 fatty acids on ocular comfort including symptoms of dry eye.	
Protocol ID Number	SOVS2016-045	
Trial Classification	Evaluation	
Investigator(s)/Site(s)	Eye Research Group @ SOVS The University of New South Wales Sydney, Australia	
Overall Duration of Trial	1 year	
Number of Trial Participants Planned	138	
Planned Start Date	February 2017	
Primary Objective	To investigate the efficacy of a nutraceutical formulation (combination of flaxseed oil, borage oil and fish oil omega-3 fatty acids) on ocular symptoms including dry eye, compared to a placebo control.	
Secondary Objective	To evaluate the safety of a nutraceutical formulation (combination of flaxseed oil, borage oil and fish oil omega-3 fatty acids) over a 3 month period.	
Primary Safety Variable(s)	Visual acuity Biomicroscopy: ocular redness, corneal and conjunctival staining	
Primary Efficacy/Performance Variable	Subjective symptom scores measured using OSDI, OCI and DEQ-5	
Experimental design	 Retrospective  Prospective  Single group  Multiple group  Parallel group  Cross over  Contralateral	 Single masked (Trial Participant)  Single masked (Investigator)  Double masked  Sponsor masked  Open label  Other

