## 12. ASSESSMENT OF SAFETY

### 12.1. Parameters

- Discomfort
- History
- Visual acuity
- Ocular redness: bulbar conjunctiva
- Corneal and conjunctival staining
- Health and wellbeing questionnaire

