### 12.4.1. Foreseeable Adverse Events

Risks associated with the use of the study product are likely to be gastric/digestive in nature and may include:

- Stomach pain (<2%)
- Diarrhoea (<1%)

Potential risks associated with the study procedures include:

- Eye irritation/discomfort (less than 1 in 20 chance)
- Watery eyes (less than 1 in 100 chance)

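### The primary safety variables are all ocular although the protocol expects gut harms from the capsule, and counts by gut symptom rest on free text and volunteered reports with no planned summary by arm

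*Combined protocol and SAP*

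**What the plan says.** **Objective and named variables.** The Protocol Synopsis (section 1, Table 1) states the secondary objective as "To evaluate the safety of a nutraceutical formulation" over 3 months. Its row for primary safety variables reads "Visual acuity Biomicroscopy: ocular redness, corneal and conjunctival staining". Nothing in that row concerns the gut or adverse events in general.

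**Expected harms.** Section 12.4.1 says: "Risks associated with the use of the study product are likely to be gastric/digestive in nature and may include". It then lists stomach pain (below 2%) and diarrhoea (below 1%). The eye irritation and watery eyes in the same section are attributed to study procedures, not to the capsule. Section 4.2.1 repeats the gastric/digestive expectation.

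**How gut symptoms are asked about.** The Health and Wellbeing Survey (Appendix II) has one gut question, item 1(c): "Experienced any Gastrointestinal irritation e.g. diarrhea, heartburn, bloating or nausea", answered Yes or No. Item 1(e) follows: "If you answered yes to any of the above, please explain". Table 4 schedules the survey at the 1-month and 3-month visits.

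**Other routes.** Section 12.1 lists "Health and wellbeing questionnaire" and history among the safety parameters. Section 12.2 has general health recorded at all visits. Section 12.3.1 counts any undesirable symptom as an adverse event, whether related or not. Section 12.4 has non-serious events recorded and all adverse events reported to the co-sponsor. Section 13.1.3 analyses safety variables over all visits, including unscheduled ones. None of these sections specifies symptom coding, severity grading or a gastrointestinal table by arm.

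**The concern.** The variables that the synopsis puts first do not match the harms that the protocol expects from the product. A safety report built on acuity, redness and staining could be clean without the foreseen gut harms having been examined.

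The instrument that does address the gut is coarse. A Yes to item 1(c) does not say which symptom occurred. Stomach pain, the foreseen harm with the higher stated ceiling, is not offered as an example. A participant with stomach pain must first decide that it counts as gastrointestinal irritation, and then name it in free text.

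At stake is how well the safety objective is answered. The protocol gives two symptom rates, but no structured field yields either count by arm. Symptom detail that is not collected at the visit is hard to recover reliably later.

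**Working it through.** **1. The plan's own figure.** Section 13.1.1 gives a difference of 10 OSDI points, SD 20, two-sided alpha 0.05 and power 80%.
- n per arm = 2 × (1.960 + 0.842)² × 20² / 10² = 62.8, so 63.
- Adding 10%: 63 × 1.1 = 69.3, which rounds to the stated 69 per arm (138 in total).

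The figure reproduces. It is sized on symptoms; the documents state no sample size or precision for safety.

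**2. Expected counts.** I assume that the section 12.4.1 percentages are per participant over the study, and I take them at their ceilings.
- Stomach pain: 0.02 × 69 = 1.38 participants.
- Diarrhoea: 0.01 × 69 = 0.69 participants.

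**3. Chance of at least one case in an arm,** 1 − (1 − p)^n, for all 69 and for 69 × 0.9 = 62 completers:

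| Symptom | p | n = 69 | n = 62 |
|---|---|---|---|
| Stomach pain | 0.02 | 0.75 | 0.71 |
| Diarrhoea | 0.01 | 0.50 | 0.46 |

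**4. What a count of zero would show.** The exact (Clopper-Pearson) two-sided 95% upper limit for 0/n is 1 − 0.025^(1/n).
- n = 69: 5.2%.
- n = 62: 5.8%.

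Both exceed 2% and 1%. The one-sided 95% limit for 0/69, 1 − 0.05^(1/69) = 4.2%, does too. These limits depend on n alone, so no redesign of the form changes them.

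**5. Sensitivity to incomplete capture.** The documents give no capture rate, so this is illustration only. If a share r of stomach-pain cases is recorded as such, the chance of recording none at the 2% ceiling is (1 − 0.02r)^69.
- r = 1: 0.98^69 = 0.25.
- r = 0.5: 0.99^69 = 0.50.

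**6. Comparison between arms.** Assumed example: 4% against 2%, 69 per arm, normal approximation (rough at such counts), with pooled rate 0.03.
- Null standard error: √(2 × 0.03 × 0.97 / 69) = 0.0290.
- Alternative standard error: √((0.04 × 0.96 + 0.02 × 0.98) / 69) = 0.0290.
- Power ≈ Φ((0.02 − 1.96 × 0.0290) / 0.0290) = Φ(−1.27), about 10%.

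**7. The capture routes side by side.**
- Item 1(c) is prompted but bundled. Item 1(e) opens only after a Yes and is free text.
- Table 4 collects adverse event data at scheduled visits only if an event is detected.
- Section 12.2 asks participants to report eye problems. Section 10.4 is broader (any problem), but still relies on the participant coming forward.
- Section 7.3.1 asks for the full 3-month assessments at early exit where possible, but its minimum set is ocular only. Someone who stops because of gut symptoms may leave without the survey.
- Table 4 marks the survey as not required at baseline, while section 12.2 has health and wellbeing assessed at all scheduled visits. If Table 4 governs, this form gives no baseline gut status. The two should be reconciled.

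**The case against.** A reader might infer that the trial cannot report the harms it foresees. The documents do not support that. Item 1(c) asks about any gastrointestinal irritation at both follow-up visits, and item 1(e) asks directly for an explanation of a Yes. History, adverse event recording and the all-visits safety analysis are further routes. Free text can be coded by symptom and tabulated by arm. The survey is itself a safety parameter in section 12.1, so the synopsis row is not the whole safety plan.

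A reader might also infer that the survey excludes stomach pain. It does not. The examples are introduced as illustrations, stomach pain fits naturally beside heartburn and bloating, and diarrhoea is named outright.

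Two further objections carry weight. The section 12.4.1 rates are statements of foreseeable risk, not targets, and no section undertakes to verify them. With about one case expected per symptom, splitting the item cannot yield a useful test between arms, and the 5.2% limit comes from 69 per arm, not from the form.

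It may also seem inconsistent to criticise a merged item and then ask for a merged variable. The two serve different purposes: any gastrointestinal symptom is a reasonable headline, while the separate lines let the reader see what it consists of.

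All of this limits the point but leaves its core. Coding free text is possible but not planned. A written explanation depends on the participant first answering Yes and then naming the symptom. The named primary variables still miss the expected type of harm.

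**Conclusion.** The point holds as a mismatch of emphasis and a weakness of structure, not as an inability to report. The primary safety variables are all ocular for an oral product whose expected harms are gastric or digestive. Gut harms can be captured, but symptom-level counts depend on free text and volunteered reports, and no gastrointestinal summary by arm is planned.

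The numbers are small: at most 1.4 stomach-pain and 0.7 diarrhoea cases expected in an arm of 69, if the stated ceilings apply per participant over the study. Individual reports therefore matter, and an observed zero is compatible with a true rate up to 5.2%. How many reports the present form would lose is unknown. The sample size is not in question.

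**What to change.** 1. In the Health and Wellbeing Survey, replace item 1(c) with separate Yes/No lines for stomach pain, diarrhoea, heartburn, bloating and nausea. Keep the free-text line 1(e) and let it also take any other gut symptom, so that the breadth of the present wording is not lost.
2. In the synopsis, add participants with any gastrointestinal symptom and participants with any adverse event, by arm, to the primary safety variables. Keep the ocular ones.
3. In section 13.1.3, state that these two variables and each gut symptom will be reported descriptively by arm with an exact 95% CI. State also that zero events in 69 has an upper limit of 5.2% and would not confirm the rates in section 12.4.1.

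**Cost.** One reprinted paper form, one synopsis row and a sentence or two in the analysis section. There is no extra visit, staff or sample size. The small downside is four more tick boxes at each of the two follow-up visits. The gain is description by symptom, not a powered comparison between arms.

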## **NUTRITION QUESTIONNAIRE**

### DIETARY SUPPLEMENTS AND OCULAR COMFORT

**ON AVERAGE, HOW MANY SERVES PER WEEK WOULD YOU EAT OF THE FOLLOWING  
(PLEASE REFER TO THE DIET GUIDE FOR FOOD TYPES WITHIN EACH GROUP AND SERVING SIZES.)**

FOOD TYPE	SERVES PER WEEK
CEREALS	
VEGETABLES, LEGUMES	
FRUIT	
MILK, YOGHURT, CHEESE	
LEAN MEAT, FISH, POULTRY, NUTS	
EXTRA FOODS (E.G. CAKES, PIES, SWEETS, SOFT DRINKS, ALCOHOL, ETC)	

**HOW MANY TIMES PER WEEK DO YOU EAT OILY FISH (SALMON, TUNA, ETC)?:** \_\_\_\_\_

**ARE YOU VEGETARIAN OR VEGAN?**

NEITHER	
VEGETARIAN (EAT FISH)	
VEGETARIAN (DO NOT EAT FISH)	
VEGAN	

## Diet Guide

## Diet Guide

### What is a serve? Here are some examples

#### Cereals, breads etc

2 slices of bread	1 medium bread roll	1 cup cooked rice, pasta, noodles
1 cup porridge	1 cup breakfast cereal flakes	or ½ cup muesli

#### Vegetables and legumes

##### Starchy vegetables

1 medium potato or yam	½ medium sweet potato	1 medium parsnip
------------------------	-----------------------	------------------

##### Dark green leafy vegetables

½ cup cabbage, spinach, silverbeet, broccoli, cauliflower or brussels sprouts

##### Legumes and other vegetables

1 cup lettuce or salad vegetables	½ cup broad beans, lentils, peas, green beans, zucchini, mushrooms, tomatoes, capsicum, cucumber, sweetcorn, turnips, swede, sprouts, celery, eggplant etc	
-----------------------------------	--	--

#### Fruit

1 piece medium sized fruit eg apple, orange, mango, mandarin, banana, pear, peach etc		
2 pieces of smaller fruit eg apricots, kiwi fruit, plums, figs	About 8 strawberries	
1 cup diced pieces or canned fruit	½ cup fruit juice	¼ medium melon (rockmelon, honeydew)
Dried fruit eg 4 dried apricots	1½ tablespoons sultanas	About 20 grapes or cherries

#### Milks, yoghurt, cheese & alternatives

250 ml glass or one cup of milk (can be fresh, longlife or reconstituted milk)		
½ cup evaporated milk	40g (2 slices) of cheese	250ml (1 cup custard)
200g (1 small carton) of yoghurt, plain or fruit, or		
a cup of calcium-fortified soy milk	1 cup almonds	½ cup pink salmon with bones

#### Meat, fish, poultry & alternatives

65-100gm cooked meat or chicken (eg ½ cup mince, 2 small chops or 2 slices roast meat)		
80-120g cooked fish fillet, or		
2 small eggs	½ cup cooked (dried) beans, lentils, chick peas, split peas or canned beans	1/3 cup peanuts or almonds

#### Extras

1 medium piece of plain cake or 1 bun	3-4 sweet biscuits	Half a chocolate bar
60g jam, honey (1 tablespoon)	30g potato crisps	Slice pizza = 2 extras
1 can soft drink or 2 glasses cordial	2 scoops icecream	1 meat pie or pasty = 3 extras
2 standard glasses of alcohol (for adults only)		

Reproduced from The Australian Guide to Healthy Eating.  
NHMRC Australian Government publication

**APPENDIX III**  
**CCLRU GRADING SCALES**

---

## APPENDIX III: CCLRU Grading Scales

---

The CCLRU Grading Scale uses a 0-4 scale in 0.5 steps, as shown in the following table:

*Table 7*

Grade	Description
0	Absent
1	Very Slight
2	Slight
3	Moderate
4	Severe

The scale is to be used in conjunction with the colour photographs as a standard to compare the observed finding and grade accordingly.

## **APPENDIX IV**

### **CIBA GRADING SCALES**

---

## APPENDIX IV: CIBA Grading Scales

---

### SLIT-LAMP QUANTIFICATION CHART

#### BIOMICROSCOPY SIGNS

##### Eyelid and Bulbar Conjunctival Redness

0	=	None: White and clear
1	=	Trace: Regional hyperemia
2	=	Mild: Diffuse hyperemia
3	=	Moderate: Marked regional or diffuse hyperemia
4	=	Severe: Diffuse episcleral or scleral hyperemia

##### Corneal Staining

0	=	None: No staining
1	=	Trace: Regional superficial stippling and/or foreign body tracks
2	=	Mild: Regional or diffuse punctate staining and/or F.B. tracks
3	=	Moderate: Dense coalescent staining and/or abrasions
4	=	Severe: Epithelial loss, or full thickness abrasion

##### Conjunctival Staining

0	=	None: No staining
1	=	Trace: Minimal regional staining
2	=	Mild: Regional or diffuse punctate staining
3	=	Moderate: Significant dense coalescent staining
4	=	Severe: Severe dense geographical staining
